PLATELET-RICH PLASMA

Platelet-rich plasma (PRP) describes an autologous blood plasma fraction, enriched with platelets, thus presenting a high concentration of protein growth factors. The extracted and prepared fluid is injected at the sight of tendon injury, theoretically acting as an adjuvant to complement and promote the natural healing process. The use of PRP in the management of musculoskeletal injuries has increased, based on in vitro studies reporting an enhancement of the recruitment, proliferation, and differentiation of the cells involved in muscular tissue regeneration.^[44]

PRP exerts it effects via the degranulation of the α -granules in platelets, which release various fundamental growth factors and cytokines; active secretion is initiated by the blood clotting process and begins within 10 minutes of clotting.^[45] As the platelets are activated, the growth factors are secreted from the cell through the cell membrane, the secreted growth factors immediately bind to the external surface of cell membranes within the wound, and in turn induce an activation of an endogenous internal signal protein, which causes the expression of a specific gene sequence of the cell such as cellular proliferation, matrix formation, osteoid production, or collagen synthesis.^[44]

Mishra *et al.* evaluated 140 patients with lateral elbow tendinopathy; patients had initially undergone a standardised physical therapy protocol and a variety of nonsurgical treatments. 20 patients experienced persistent pain and failed to respond adequately, this cohort were then given either a single percutaneous injection of platelet-rich plasma or bupivacaine as a control.^[48] Eight weeks post-injection, the study group reported a 60% improvement in pain

compared with a 16% improvement in the control group. At six months response within study group had increased to 80% improvement.

De Vos *et al.* recently published a systematic review of PRP injections for chronic lateral epicondyle tendinopathy.^[46] Five of the six studies included found no significant benefit in the study group compared with their respective controls at follow-up. The final study showed a beneficial effect compared with corticosteroid injection.

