- Ipsilateral arm pathology severe enough to cause confusion of localised pain perception.
- Pregnancy, lactating women, local infection.
- Pain score less than 4/10
- Patients commenced on medication for the treatment of anxiety or depression within the last 6 weeks
- Previous involved in research in last 12 months
- Any progressive, degenerative neuromuscular disorder

Withdrawal Criteria.

Patients may be withdrawn from the study when:

- Patient expresses desire to withdraw.
- Major repeated protocol deviation
- Non-compliance of patient

Adverse event and Side Effect Reporting.

Any adverse event reported by a participating patient to a member of the clinical care team at any follow up visit, or between visits to the patient's GP or other physician will be recorded and detailed in an AE report. The lead investigator will examine the reporting patient as soon as possible following the generation of a report and where appropriate, order any tests or prescribe such medicines or treatment as deemed to be necessary.

If any patient is admitted via Accident & Emergency for any reason either connected or unconnected with the study, either the lead investigator or a designated member of the clinical care team will liaise with the appropriate Consulting clinician. The details of any reported AE will be specified in terms of subjectively reported symptoms and sensations, along with a qualified medical opinion from either the lead investigator or a designated member of the clinical care team as to likely cause of any signs or symptoms presenting at examination. Where diagnostic tests (e.g. blood tests, laboratory cultures) are ordered, a copy of the test results will be appended to the patient record card. Following due scrutiny, any side effects in either study group will be determined as either; 1. Unrelated to study treatment in any way. 2. Related to injection (needle placement, injection site reaction to needling, infection). 3. Related to local anaesthetic, as designated on the summary of product characteristics under known side effects. 4. Related to PRP, as designated on the summary of product characteristics under known side effects. 5. Related to Ostenil Tendon[™], as designated on the summary of product characteristics under known side effects.

Procedure.

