Consenting participants will be randomised to Study Group A (physio and PRP), Study Group B (physio and Ostenil Tendon[™]), or Control Group C (physio and sham injection) once informed consent has been recorded and baseline data has been collected.

Treatment and follow-up will be the same for those patients who wish to take part in the study and for those patients who decline to take part but whose condition makes a peri-tendinous injection clinically appropriate. Following informed consent, patients will be assessed for demographic detail (age, gender, ethnicity, occupation, affected elbow, height and weight/BMI, duration of symptoms, relevant diagnosis, current medication), and given patient completed questionnaires to assess pain and function (Oxford Elbow Score (OES), Quick DASH Score, 100 mm visual analogue pain scale with terminal descriptors), Hospital Anxiety and Depression (HAD) Score and asked to complete EQ5D at the initial consultation (V1).

Treatment: Consenting patients will attend for the injection to be administered under ultrasound guidance. All participants will have 30ml of whole venous blood withdrawn under aseptic conditions.

Out of sight of the patient the whole venous blood will either be;

placed in the cell separator and centrifuged at 32000 rpm for 15 minutes for subjects in group A. During the centrifugation process 2ml of 2% plain lidocaine will be injected into the subcutaneous layer at the site of injection of the PRP. One millilitre (2ml) of PRP produced will be drawn into a syringe wrapped in silver foil and injected under ultrasound control via a blue (20 gauge) hypodermic needle into the lateral epicondyle using a peppering technique.

Or

discarded for those in group B and C. The centrifuge will be set to run at 32000rpm for 15 minutes with a saline counterbalance. During the centrifugation process 2ml of 2% plain lidocaine will be injected into the subcutaneous layer at the site of injection. For those in group B a pre-prepared "Ostenil Tendon" syringe will be wrapped in silver foil and 2ml will be injected into the peri-tendinous area via a blue (20 gauge) hypodermic needle under ultrasound control.

For those in group C an empty syringe wrapped in silver foil with a blue (20 gauge) hypodermic needle will be used to perform a sham injection into the subcutaneous tissue only by passing the needle into the tissue with no injectate.

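### The final adverse-event classification allows a product cause only for side effects already listed, so a genuine but unlisted product reaction has no correct category

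*Combined protocol and SAP*

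**What the plan says.** The rule is in the protocol under Adverse event and Side Effect Reporting. Events are written up in a report that includes a medical opinion on probable cause, given by the lead investigator or a delegated member of the clinical team. On who sees the patient, the section says: "The lead investigator will examine the reporting patient as soon as possible following the generation of a report". A final classification follows: "any side effects in either study group will be determined as either" one of five numbered categories.

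- Category 1 is "Unrelated to study treatment in any way".
- Category 2 is "Related to injection (needle placement, injection site reaction to needling, infection".
- Categories 3, 4 and 5 are the local anaesthetic, PRP and Ostenil Tendon. Each is tied to the side effects listed for that product. For PRP the wording is "Related to PRP, as designated on the summary of product characteristics under known side effects".

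The list has no category for other, unexpected, possible or unknown causes. Elsewhere the protocol describes PRP as "an autologous blood plasma fraction, enriched with platelets". Under Procedure (Treatment) it states: "All participants will have 30ml of whole venous blood withdrawn under aseptic conditions". Under Physiotherapy protocol, every patient starts eccentric loading exercises the day after injection.

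**The concern.** Relatedness and expectedness are different judgements. Relatedness asks whether the exposure caused the event. Expectedness asks whether the event already appears in the reference information. This scheme makes the second a condition of the first for all three products. The events that fall outside it are those that safety recording most needs to bring out: reactions to a product that nobody has listed yet.

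This is a stated rule and not a missing detail, because the categories are written out and closed. It is also the only coded causality result in the plan. The lists of primary and secondary outcomes contain no safety measure, and Statistical Analysis does not mention adverse events. If the code is wrong or cannot be assigned, no other structured item recovers the attribution.

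**Working it through.** No calculation bears on the main point. The check is to set the five categories side by side and ask where particular events would go.

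| Category | Cause named | Must the effect already be listed? | Further limit |
|---|---|---|---|
| 1 | None | No | Must be unconnected with study treatment altogether |
| 2 | Injection | No | Needle placement, needling reaction, infection |
| 3 | Local anaesthetic | Yes | None |
| 4 | PRP | Yes | None |
| 5 | Ostenil Tendon | Yes | None |

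**Step 1: an unlisted reaction to PRP or Ostenil Tendon.** Categories 4 and 5 are closed to it because it is not listed. Category 3 names a different product. Category 2 covers needling and infection only. Category 1 is false, because the event is related. No category is correct. The same holds for an unlisted reaction to the local anaesthetic, which all three arms receive.

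**Step 2: is there an outlet elsewhere?** The rest of the document contains no separate assessment of expectedness and no procedure for unexpected reactions. The only outlet is the narrative opinion on likely cause. It is not tied to any list, but it is free text and it precedes the coding.

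**Step 3: other study exposures.** The 30 ml blood draw and the exercise programme apply to everyone. A reaction at the blood-draw site is not an injection or product effect, and neither is a strain from the exercises. Category 1 does not fit either, since both are study procedures.

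**Step 4: which arms are covered.** The scheme speaks of either study group. Under Procedure the arms are Study Group A, Study Group B and Control Group C, so the phrase can be read as leaving out the sham arm. Under Interventions the third arm is called Study Group C, so it can also be read as including it. The text does not settle this.

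**Step 5: the blind.** Choosing between categories 4 and 5 means naming the product received. The roles stated to be blinded are the physiotherapist and the clinician who assesses at 3 and 12 months. Nothing says whether the person who classifies events is blinded, whether that person also scores outcomes, or when the classification is done.

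**Size.** The documents give no adverse-event rate, so an expected number of uncodable events cannot be derived. For scale only: the planned total of 123 gives 123/3 = 41 per arm, so one patient is 1/41 = 2.4% of an arm. That is the weight of a single event and not a forecast that any will occur.

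**The case against.** The strongest answer is the narrative opinion, required in the same section. An assessor who thinks PRP caused an unlisted reaction can say so there. This stands: a reader might infer that no unlisted reaction can ever be recorded as product-related, and that is true only of the final code.

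A reader might also infer that unlisted reactions must be filed as unrelated or as needle-related. The text does not instruct that. Read strictly, both categories exclude such an event. Misfiling is what an assessor might do when faced with a closed list, but it is not what the rule says.

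Three further readings go beyond the documents.

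- **Classification breaks the blind.** This would need the classifier to be a blinded outcome assessor, and the documents do not say so. Unblinded staff could do it, or it could be done after unblinding.
- **The safety comparison with sham is distorted.** The plan contains no comparative safety analysis. Reported events are recorded whatever their code, so all-cause counts by arm are unaffected.
- **PRP has no reference list, so category 4 is empty.** The protocol identifies none, but it reproduces no side-effect list for lidocaine or Ostenil Tendon either. Whether a reference document for PRP exists cannot be settled from the text.

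Finally, the limiting clause could be taken as a loose pointer to a reference document and not as a condition. That is possible, but it is not the plain meaning, and nothing else in the protocol supports it.

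**Conclusion.** The point holds as a defect in the final classification. The list is closed, its three product categories all require the effect to be listed already, and a genuine but unlisted product reaction has no correct place in it. The product attribution then survives only as narrative. The missing categories for the blood draw and the exercise programme, and the unclear coverage of the sham arm, are smaller faults in the same paragraph.

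The conclusion rests on the plain reading of the limiting clause and on the absence of any other rule for unexpected reactions in the document. The number of events affected cannot be estimated. Risk to the blind is an open question that the protocol should answer, not a demonstrated fault. The primary outcome, QuickDASH at 12 months, is not touched, and neither is the capture of events. The change is worth making because the rule is wrong as written and cheap to correct.

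**What to change.** Reword the paragraph and the adverse-event form as follows.

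1. Remove from the relatedness categories the clause that limits them to listed side effects.
2. Record relatedness separately for each exposure: blood draw, local anaesthetic, study injection (product not named) and physiotherapy. Do this whether or not the effect is listed.
3. Record expectedness in its own field, against named reference information for each product, and say what that reference is for PRP. Have it completed by staff who are already unblinded, or after unblinding.
4. State who makes each judgement and whether that person is blinded.
5. State that the scheme applies to all three arms, and tabulate related events by arm.

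Leaving the product unnamed loses nothing at analysis, because the allocation supplies it. Differences between arms in injection-related events will still mix product with technique: PRP is given by peppering, Ostenil Tendon around the tendon, and the sham under the skin only. That follows from the design, and the table should carry a note to that effect.

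The cost is one reworded paragraph, a revised form and one extra table. No patients or visits are added.

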Over 80% of patients with lateral epicondyle tendinopathy report improvement within 1 year, which supports the often adopted wait-and-see policy.^[7] Within this period, workload and activity modification is recommended to remove any exacerbating stimulus, relieve strain and allow time for healing.^[12] Topical non-steroidal anti-inflammatory drugs (NSAIDs) may provide beneficial relief from pain compared with placebo in the short term (3-4 weeks)^[13-16]. Oral NSAIDs have not been found to provide longer-term effects (> 4 weeks), however the risk of gastro-intestinal adverse effects is significantly increased.^[13-17] The Cochrane review of NSAIDs for treating lateral elbow pain concludes that evidence on which to base recommendations for the longer-term use of NSAIDs is insufficient.^[14] Local corticosteroid injections have been found to provide beneficial short-term therapeutic effect (< 6 weeks), however this was not continued into the intermediate (6 weeks to 6 months) or longer (> 6 months) terms.^[15,18-19] Biset *et al.* found corticosteroid injection to be superior compared with physiotherapy at 6 weeks, however high reoccurrence rates were observed (47 of 65 patients deemed initial successes subsequently represented), and long term outcomes were found to be significantly poorer compared with physiotherapy.^[20] Adverse effects include: post-injection pain, skin depigmentation, subcutaneous fat atrophy, and, in some instances, tendon and ligament rupture.^[21,22]

HYALURONIC ACID

Hyaluronic acid (HA) is a naturally occurring polymer, ubiquitous to the human body. HA, in its aggregated form, is an important structural component of the articular cartilage matrix, imbibing water molecules to provide cartilage resilience to compressive forces. Unaggregated, HA is the main macro-molecular constituent of synovial fluid and is fundamental to its characteristic viscoelastic properties. This enables the intra-articular fluid to function as a lubricant and a shock absorber between congruent cartilaginous surfaces. HA does not only

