During the procedure the patient will be distracted by being asked to confirm their personal details.

Patients will be given pain report diaries which will be completed on days 1, 2, 3, 7, and 14, and at 6 weeks, 12 weeks (final clinical follow up visit prior to discharge).-Patients will be taught home exercises by a blinded physiotherapist prior to discharge, a formal class based physiotherapy programme will commence at 5-15 days post injection. The patient will be assessed by a blinded clinician at 3 months and 12 months post treatment. Telephone follow-up calls will be made to patients 3 months and 12 months post treatment if the patient declines to attend a follow-up appointment. The Consulting physician will discharge patients from his direct care at 12 weeks unless enduring or subsequently manifesting symptoms persist. Pain scores, amount of rescue medication (codeine & Paracetamol) and QOL questionnaires will be completed at all visits. The OES, qDASH, HAD and EQ5D will be completed at 3 and 12 month reviews.

Patients who successfully complete both 3 month and 12 months outcome questionnaires with be entered into a raffle to win an iPad tablet computer.

Primary Measure of Outcome.

The difference in Objective Functional Assessment as evinced by Quick DASH, at 12 months

Secondary Measures of Outcome.

The difference in Objective Pain and Functional Assessment as evinced by OES and 100 point VAS with terminal descriptors at 12 months

Change in EQ5D General Health Questionnaire.

Relationship of pre-injection HAD score to outcome.

Change in HAD score at 12months

Use of Rescue Medication.

Number of Patients.

The proposed randomized controlled double blind (single centre) trial design will have 80% power (1- β) to reject the null hypothesis, with an α (type I error, i.e. level of statistical significance) set at 0.05. Assuming a clinically significant [mean] difference (δ) of 15 Q-DASH score units between groups together with an estimated sample standard deviation (σ) of 22.5 (Biomet study – based on Q-DASH score for PRP arm) which gives an 'n' for each trial arm (assuming equal group sizes) of at least 35 analyzable patients in each of the three groups (A,B &C) and given a possible attrition rate of about 16% the CITTE trial will probably therefore need a total sample size of at least 123 of patients, approximately.

Statistical Analysis.

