All quantitative data - age, gender, duration of symptoms, disease progression, target joint, Height, weight and BMI, will be analysed using the most appropriate non-parametric tests. VAS, qDASH and OES score Inventories, EQ5D, Blinded Assessor and escape medication scores will be tested for homogeneity of variance (Chi sq/F test), mean scores calculated, and then either *t* tested (with possible ANOVA for correlations between pain, function, strength etc) or Mann-Whitney/ Wilcoxon rank sum (Kruskall Wallis differences /Jonkheere trend).

Interventions

Physiotherapy protocol

After the injection and prior to discharge a physiotherapist will teach patients eccentric loading exercises of the wrist extensors. They will be instructed to commence the exercises at day 1 post injection. They will be advised to carry out 3 sets of 15 repetitions, 3 times per day. An accompanying exercise sheet will advise to increase the load as symptoms permit. It will be suggested to commence with a half filled 500ml bottle of water. In addition a simple common extensor stretch will be taught to use following the eccentric exercises.

At 5-15 days post injection the patients will commence an out-patient class based physiotherapy programme. The class will be held 2 weekly by a blinded physiotherapist. After being taught the exercises on an 1:1 basis, the patients will be supervised during a circuit style exercise programme. The exercise programme will include eccentric loading of the common extensors, and upper limb strengthening involving the full kinetic chain, in particular the rotator cuff and scapular muscles. Each patient will be supervised and monitored to improve technique, and to increase the load. Patients will be provided with a home exercise programme which will reflect the class exercises.

Study GROUP A Product Dose, Presentation, and Mode of Administration.

2ml unbuffered PRP prepared with **Zimmer/Biomet Recover Mini-platelet** system administered via intratendinous injection under ultrasound.

Study GROUP B Product Dose, Presentation, and Mode of Administration.

Ostenil[™] Tendon (40mg/2ml of bio-fermentation source Sodium Hyaluronate with 10mg Mannitol in a pre-filled syringe). To be administered via peritendinous injection under ultrasound.

Licensed indication in the EU: For the treatment of pain and restricted mobility in tendon disorders.

Active Ingredient; Sodium Hyaluronate / Mannitol

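### QuickDASH is measured at baseline, 3 and 12 months, but the plan names no analysis that uses the earlier scores and no method for missing 12-month scores

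*Combined protocol and SAP*

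**What the plan says.** All references are to the protocol, which also holds the analysis plan.

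- **Collection.** Under Procedure, QuickDASH, OES, pain VAS, HAD and EQ5D are taken at the initial consultation. After treatment: "The OES, qDASH, HAD and EQ5D will be completed at 3 and 12 month reviews". Also: "Pain scores, amount of rescue medication (codeine & Paracetamol) and QOL questionnaires will be completed at all visits". A separate pain diary is "completed on days 1, 2, 3, 7, and 14, and at 6 weeks, 12 weeks", which is seven dates and pain only.
- **Outcomes.** The primary measure is "The difference in Objective Functional Assessment as evinced by Quick DASH, at 12 months". The secondary pain and function measure is "evinced by OES and 100 point VAS with terminal descriptors at 12 months". Change in HAD is at 12 months. Change in EQ5D and use of rescue medication have no time point.
- **Analysis.** Under Statistical Analysis, the VAS, QuickDASH, OES, EQ5D and rescue medication scores "will be tested for homogeneity of variance (Chi sq/F test), mean scores calculated, and then either" compared by t test or by rank tests. No visit is specified. No repeated-measures model, baseline covariate or rule for missing scores appears.
- **Loss.** Under Number of Patients, the total of 123 is reached from 35 analysable patients per arm, "given a possible attrition rate of about 16" per cent.

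**The concern.** A t or rank test on the 12-month QuickDASH can use only patients who have that score. A patient lost after 3 months contributes nothing to it, even though two QuickDASH scores are on file. This has three consequences.

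**Bias.** If the chance of returning at 12 months depends on status at 3 months, those who return are a selected group, and the selection may differ by arm. The protocol makes this plausible: patients are discharged at 12 weeks unless symptoms persist. A model that contains the 3-month score can correct for such loss; a test on the remaining patients cannot.

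**Precision.** Baseline and 3-month scores predict the 12-month score to some degree, and ignoring them widens the interval.

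**Pre-specification.** The background section states that "Over 80% of patients with lateral epicondyle tendinopathy report improvement within 1 year", so arms could converge by the primary time point. The 3-month scores would show whether one arm recovered sooner, yet no 3-month QuickDASH, OES or VAS comparison is a named outcome. If early comparisons are chosen after the data are seen, a reader cannot tell a planned result from a selected one.

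**Working it through.** **Inputs from Number of Patients.** Difference 15 QuickDASH units, SD 22.5, alpha 0.05 (taken as two-sided; the text does not say), power 80%, 35 analysable per arm, attrition about 16%, total 123.

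**Assumed inputs, not in the documents.** Correlation of 3-month with 12-month QuickDASH 0.4 to 0.8; correlation of baseline with 12-month QuickDASH 0.3 to 0.6; half or all of those lost by 12 months having a 3-month score.

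**1. The plan's own figures.** n per arm = 2 × [(1.96 + 0.84) × 22.5 / 15]² = 35.3, against the stated 35. With attrition, 35 × 1.16 = 40.6, rounded up to 41, and 3 × 41 = 123. Both are reproduced, and this point does not affect the total.

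**2. Patients with a 12-month score.** Overall loss is 123 × 0.16 = 19.7, about 20 patients. Per arm, m = 41 × 0.84 = 34.4 remain. A two-sample t test then has power 77.8% (79.0% by the normal approximation).

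**3. Adding 3-month scores.** If loss depends only on observed scores, the variance of an arm's 12-month mean is

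σ² × [(1 − ρ²)/m + ρ²/n₃],

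where n₃ is the number in the arm with a 3-month score: 41 if all those lost have one, 34.4 + 0.5 × 6.6 = 37.7 if half do. For ρ = 0.8 with all: 0.36/34.44 + 0.64/41 = 0.02606, against 1/34.44 = 0.02904 without 3-month scores. The variance falls by 10.2% and the effective n is 1/0.02606 = 38.4.

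| Share of those lost who have a 3-month score | ρ | Effective n per arm | Variance cut | Power (t) |
|---|---|---|---|---|
| Half | 0.4 | 34.9 | 1.4% | 78.4% |
| Half | 0.8 | 36.5 | 5.6% | 80.2% |
| All | 0.4 | 35.3 | 2.6% | 78.9% |
| All | 0.8 | 38.4 | 10.2% | 82.2% |

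**4. Baseline adjustment, taken separately.** Adjusting for baseline multiplies the variance by 1 − ρ². At 34 per arm, unadjusted power is 77.3%. With ρ = 0.3, 0.5 and 0.6 the SD becomes 22.5 × √0.91 = 21.5, 22.5 × √0.75 = 19.5 and 22.5 × √0.64 = 18.0. Power becomes 81.0%, 87.8% and 92.3%. The gains in steps 3 and 4 should not be added: once baseline is in the model, part of what the 3-month score carries is already used.

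**5. Size of a possible bias, as illustration only.** Suppose patients lost from one arm are 10 points worse at 12 months than those kept, and in the other arm there is no gap. The between-arm difference is then off by 0.16 × 10 = 1.6 points, or 1.6/15 = 11% of the target difference. If loss depends on the 3-month score, and those lost have one, a correctly specified model removes this. If loss depends on the unseen 12-month score itself, roughly 1 − ρ² of it stays: 0.84 × 1.6 = 1.3 points at ρ = 0.4, or 0.36 × 1.6 = 0.6 points at ρ = 0.8.

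**The case against.** The strongest reply is that the plan is brief rather than wrong. A single 12-month primary time point is a legitimate choice. Missing data are not mentioned, so an analysis restricted to patients with a 12-month score is nowhere stated. Telephone calls at 3 and 12 months for patients who decline to attend, and a raffle tied to completing both questionnaires, may keep loss below 16%, which the protocol itself calls only possible. The precision recovered from 3-month scores is small, the correlations are assumed, and the 10-point gap has no source in the documents.

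Much of this stands. The 12-month primary should stay, and precision from 3-month scores alone would not justify a change. The inference about which patients are analysed is nevertheless strong: the sample size counts analysable patients and adds a margin for loss, and the listed tests cannot use a patient without the score. Better retention lowers the loss but does not say how to analyse what is still missing.

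A reader might infer more than the text supports:

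- That QuickDASH and OES are recorded on the seven diary dates. They are not; their only intermediate point is 3 months.
- That the early data are wasted, or that faster recovery could not be seen. The analysis section does not restrict testing to 12 months, and EQ5D and rescue medication have no fixed time point, so 3-month comparisons are permitted. The fault is that they are not specified.
- That the rise to 81%-92% power comes from the 3-month or diary data. It comes entirely from baseline adjustment.

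**Conclusion.** The point holds as a gap in method and pre-specification. The plan gives no analysis in which baseline or 3-month QuickDASH informs the 12-month comparison, and no method for missing 12-month scores, with about 20 of 123 patients possibly affected. Visit-by-visit tests, though permitted, would not close this gap, because each would still ignore the other visits.

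On precision, the 3-month scores are worth about 0.6 to 4.4 power points (77.8% to 78.4%-82.2%). The separate gain from baseline adjustment is larger. Both ranges rest on assumed correlations. The direction and size of any bias cannot be known from the documents; the 1.6-point figure only shows the scale under one assumed pattern of loss.

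This should be changed before unblinded data are seen. It does not invalidate the design or the sample size.

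**What to change.** Analyse QuickDASH with one mixed model for repeated measures. Include arm, visit (3 and 12 months), arm-by-visit, baseline QuickDASH and baseline-by-visit, in all randomised patients with at least one follow-up score.

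- Keep the 12-month between-arm contrast as primary.
- Name the 3-month contrast from the same model as a secondary outcome.
- Add one sensitivity analysis that shifts unobserved 12-month scores by a stated amount per arm, with the amounts fixed in advance.
- A diary-pain summary is optional. If one is used, define it in advance and weight it by time, because the dates are unevenly spaced and a simple mean would favour days 1 to 3.

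The cost is revised analysis wording and some programming. The model assumes that loss depends only on observed scores. Bias from loss that depends on the unseen 12-month score is only partly removed, which is why the sensitivity analysis is needed. Patients lost before 3 months are still excluded, and their number should be reported by arm.
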